7.6.2. To explore how the MSK-Tracker changes the nature of consultation conversations

To evaluate the impact of the MSK-Tracker on the consultation in respect to the focus of what is discussed with the patient, we will use audio recordings of a purposive sample of approximately 20 consultations from Stage 1 and again approximately 20 consultations from Stage 3, where patients and clinicians provide consent, in order to examine the content of what is discussed during the consultation. In particular we will examine the proportion of time in both phases spent in discussing;

the biomedical cause of the symptoms, the patient's treatment options, ways in which the patient can self-manage, return to work or support at work issues, specific concerns identified by the patient, and aspects of long-term management beyond the immediate consultation. A descriptive content analysis will be conducted by a qualitative researcher to identify differences between phase 1 and phase 3.

Recruitment and consent – for the consultation recording: The study patient information leaflet sent to patients at the start of the study will alert patient to the fact that they may be asked if their consultation can be audio recorded. On attending clinic, patients taking part in the study will be asked by their clinician if they consent to the audio recording of their consultation. Consent will be recorded on the Tracker and consent will be checked with the patient again at the end of the recording ensuring patients can change their mind easily.

7.6.3. Individual interviews with patients and clinicians to explore experiences of the MSK-Tracker

Baseline patient interviews in phase 1 will establish a baseline and map current experiences of clinic consultations and patient empowerment through supported self-management. The experience based co design (EBCD) (reference: <https://www.ncbi.nlm.nih.gov/pmc/articles/PMC2565809/>) will be applied. Patient recruitment: Following completion of their 2-week follow-up questionnaire online, patients will be asked if they are willing to take part in additional related research. A link to an online patient information leaflet will be available providing detailed information relating to the interview (see section 7.2 for full details of consent). We will seek to interview approximately 10 patients. Patients will be asked if they are able to be interviewed over the telephone or via Skype about their clinic experiences.

Baseline clinician interviews at the end of Phase 1 and prior to the beginning of the phase 2 clinician interviews will be used to establish a baseline and map current experiences of clinicians' views of consulting with MSK patients and empowering patients through supported self-management and better healthcare planning. Individual clinicians taking part in the MSK-Tracker study will be provided with a participant information leaflet and consent form and will be asked to return the consent form to the research team informing them when would be convenient to contact them for their interview over the telephone/via Skype. The EBCD approach will again be applied (approximately 10 clinicians). Building on existing insight into the aspects of consultations that matter to patients and clinicians, this baseline will establish clinicians' experiences of consultations without the MSK-Tracker being available.

There will be 10 touchpoints covered. The clinician and patient interviews will cover the same or extremely similar touchpoints so that we have a 360 degree perspective on the conversation.

The full list of touchpoints is given below. Supported by our regular PPIE involvement in the study and our clinician expert advisors, this full list will be shortlisted to 10 touchpoints:

1. Establishing rapport and setting the clinic agenda; exploring and understanding what matters to me (patients)
2. Getting "must do" work done (clinicians only)
3. Getting to the bottom of the story
4. (Educating and providing information) being educated; getting information I need
5. (Supporting) improving self-management

6. (Explaining) understanding test results, clinical measures and terms in simple words
7. (Explaining) understanding the options; making choices
8. Sharing decisions; making changes
9. Setting goals and personal outcomes
10. Getting to know each other; feeling understood i.e. relationships between patients and clinicians
11. Learning from one another; experiencing “lightbulb moments”
12. Working with technology and IT in clinic
13. Documenting treatments and actions (clinician only)
14. Reflections after the appointment
15. Professional fulfilment (clinician only)
16. Satisfaction with the quality of the clinic conversation
17. Progressing towards personal goals and outcomes

The discovery process applied with both groups around these touchpoints will enable personal reflection and discussion, and will focus heavily on how each party feels (including negative emotions and fears as well as positive emotions like hope, inspiration and trust). It will also capture perceptions of the clinic conversation process and any contextual factors that people perceive impact on the nature of the clinic conversation and what happens after.

In addition, clinicians will be asked the following open questions:

- What is the best thing about your current clinic conversations with patients?
- What is the worst thing about your current clinic conversations with patients?
- What helps you have person centred conversations?
- What hinders you having person centred conversations?
- What is the one thing you would change so you can have more person centred conversations?

In addition, patients will be asked the following open questions:

- What is the best thing about your current clinic conversations?
- What is the worst thing about your current clinic conversations?
- What helps you share what matters to you in clinic appointments?
- What hinders you sharing what matters to you in clinic appointments?
- What is the one thing you would change so you and your clinician focus more on what matters to you?

Follow up interviews in Phase 3

Patients and clinicians will also be interviewed during phase 3 to establish whether and how the introduction of MSK-Tracker has altered their perceived experience of clinic conversations and patients’ ability to take control of their health issues. Patient and clinician recruitment will mirror the processes used in phase 1. The follow up questions will mirror the same shortlisted 10 touchpoints,

agreed at baseline, so comparison is possible, only adding their views about the influence of the MSK-Tracker on their MSK consultations. The following guide will be used:

With clinicians:

- What is the best thing about using MSK-Tracker in clinic conversations with patients?
- What is the worst thing about using MSK-Tracker in clinic conversations with patients?
- How does MSK-Tracker help you focus on and have more person-centred conversations?
- What gets in the way of MSK-Tracker supporting person-centred conversations?
- What is the one thing you would change about MSK-Tracker so that it supports you to have even more person-centred conversations?

With patients:

- What is the best thing about using MSK-Tracker in clinic conversations?
- What is the worst thing about using MSK-Tracker in clinic conversations?
- How does MSK-Tracker help you focus on and share what matters to you in clinic conversations?
- What gets in the way of MSK-Tracker supporting you to share what matters to you in clinic appointments?
- What is the one thing you would change about MSK-Tracker so that you and your clinician focus even more on what matters to you?

With both parties and where individuals are interested in exploring these questions, researchers will also capture:

- What surprised people about how MSK-Tracker changed things
- What resonated with peoples' previous experiences
- What people learnt from using the tool
- What people will stop, start and continue to do
- Advice to researchers and others around scaling up MSK-Tracker (including identification of particularly appropriate or inappropriate patient groups to use the Tracker).

7.6.4. To explore how MSK-Tracker aggregated data informs service quality improvement

It is anticipated that the MSK-Tracker, as well as empowering patients, will be useful for generating aggregated feedback about what matters to patients that MSK Service providers (and potentially commissioners) can use to support continuous quality improvement.

For the purposes of this study, anonymised data generated from MSK-Tracker will be combined with insights generated from the EBCD research programme as this mirrors what would be possible in the real world.

The research team has already conducted a Stakeholder Workshop with service provider leads, commissioners and PPIE group representatives and explored what matters to them in relation to great Quality Improvement (QI) insight.

The key findings were the MSK-Tracker QI data set should immediately:

1. Be designed for three end users, with data presented in formats that are easy to use for each group:
 - The individual person and their support circle
 - The provider and their front line clinical teams
 - Commissioners and others who manage the whole system at a clinical site level
2. Include an equal balance of qualitative and quantitative data
3. Focus on what matters to patients, most especially their emotional journey and supporting the enablers that help them to improve their lives

The research team have responded to these three immediate recommendations.

The group also recommended that in time in the future (beyond the life of this study), the MSK-Tracker QI data set should aim to:

- Enable MSK-Tracker QI data to be triangulated with National Health Service (NHS) service use data and/or patients' self-reported service use data so that the whole system impacts of introducing MSK-Tracker can be measured as part of routine/real time business intelligence
- Explore the potential for MSK-Tracker to generate feedback from staff to support reflective practice at the end of clinic conversations
- Look at how partners, spouses or other family carers who are an important source of support for patients can access the tool with permission from patient
- Ensure data collection can continue beyond 3 months.

Building on the findings from the Stakeholder Workshop we have already held with service provider leads, commissioners and PPIE group representatives, this EBCD programme will have two phases using two workshops;

1. The Experience Led Commissioning (ELC) Programme (www.elcworks.co.uk) – experts in quality improvement and in interpreting and translating patient and staff feedback into actionable improvement insights - will run a joint workshop with a co-design team of PPIE members and end user clinicians and managers, including organisational and clinical leads from the MSK interface service and present a 'mock up' presentation of QI insight, aimed at the three end users. The MSK-Tracker development team and the software provider will also attend the workshop so that they can hear discussions first hand.

Our co-design team of experts by experience will positively challenge and improve the presentation of the QI data, feeding back what they like about it and what they would like to see change and improve. They will also reflect on what they might stop, start and continue to do when they have business intelligence of this kind available to them.

2. Towards the end of phase 3, researchers will analyse anonymised data and combine insights generated (downloaded) from MSK-Tracker (including PROMs, process and activity data) with insights gained from the qualitative EBCD insights generated from frontline clinicians and patients' experience of clinic conversations with and without MSK-Tracker.

Building on the feedback from the initial co-design workshop, The ELC Programme will present the QI data for the three end user groups as actionable insights so that those leading delivery and improvement of the local MSK service can use this information for quality improvement purposes.

This will happen at a QI Challenge Workshop with local service leaders, clinicians and patients at each participating site. All stakeholders will have the opportunity to work with their QI data, and respond with key improvement actions. In a safe space for reflection and exploration, workshop participants will discuss whether the findings are in line with their expectations; their perceptions of what might underpin and explain their performance, and whether and how they can use the feedback to influence quality improvement going forward.

They will also feed back to the research team and the ELC Programme their thoughts about the trustworthiness, credibility, value, usability and utility of the QI insights and how their presentation and utility can be further improved. This will in turn inform the design of the MSK-Tracker and recommendations around how it can be harnessed to support quality improvement at personal, service provider and whole system levels. Following this workshop, where data is already available, the final QI report will be improved so that the team's understanding about what such a report should contain for maxim utility is not lost.

7.7 Withdrawal criteria

Patients can withdraw at any time. Withdrawal will mean no further reminders or emails to complete online questionnaires will be sent. Any information provided up to the point they withdraw will be used unless the patients asks for their data to be destroyed.

7.8 End of study

The study end point is either when the last participant recruited in phase 3 completes their 3 month follow up, or the final qualitative interview or workshop is completed (whichever is last).

8 STATISTICS AND DATA ANALYSIS

8.1 Sample size calculation

The primary outcome of this trial is the patient enablement instrument (PEI) at 2 week follow up. As patients are asked to retrospectively rate the level of enablement, at the 2-week follow up, as a result of their visit to the Staffordshire Musculoskeletal Interface Service we only have a score at a single time point (and not a change score) for each group of patients in Phase 1 and Phase 3. The Patient Enablement Instrument consists of six items graded on three-point scales. It is scored between 0 and 12 and a high score represents more enablement. The sample size was generated based on that required for an independent groups two-sample t-test with a two tailed 5% significance level at 80% power. As no Minimally Clinically Important Difference (MCID) relevant to the specific context could be found for the PEI, the study is powered to find a 0.40 effect size – representative of a small to medium effect. The expected SD for the population is 3.86 thus, the implied MCID between the groups would be a score of 1.55 scale points. Accordingly, the required sample is 100 in each arm. If we account for 50% dropout and missingness, the target recruitment is 200 in both phases 1 and 3.

8.2 Planned recruitment rate

The target recruitment will be 200 participants (in both phase 1 and phase 3).

8.3 Statistical analysis plan

Initially, descriptive data will characterise the study sample. A descriptive statistical analysis will provide estimates of the extent to which, between phase 1 and phase 3, the use of the MSK-Tracker changed the content and time spent on topics of patient concern in the clinic consultations. A formal hypothesis testing of the effectiveness of the MSK-Tracker to empower patients using the patient

enablement scale will be conducted. Estimates of mean differences will be calculated between phase 1 and phase 3 with 95% confidence intervals (and with adjustment for any important differences between phase 1 and phase 3 participants, if appropriate). Additionally, by calculating between-group effect sizes on a range of clinical outcomes, the analysis will seek to identify on which outcomes the MSK-Tracker implementation has had impact. If a clinically meaningful difference on an outcome lies within the confidence interval, this will support evidence of an effect of the MSK-Tracker. Changes in clinician behaviours reported on the case report forms will be examined to test if there are significant differences in these behaviours between 'before' and 'after' phases i.e. phase 1 and phase 3.

Feasibility will be determined if greater than 50% of both patients and clinicians agree that the MSK-Tracker is acceptable and useful in routine clinical care based on items in the 3 month follow-up questionnaire to patients, and the interviews with patients and clinicians in phase 3.

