The primary outcome of this trial is the patient enablement instrument (PEI)¹ at 2 week follow up. As patients are asked to retrospectively rate the level of enablement, at the 2-week follow up, as a result of their visit to the Staffordshire Musculoskeletal Interface Service we only have a score at a single time point (and not a change score) for each group of patients in Phase 1 and Phase 3. The Patient Enablement Instrument consists of six items graded on three-point scales. It is scored between 0 and 12 and a high score represents more enablement. The sample size was generated based on that required for an independent groups two-sample t-test with a two tailed 5% significance level at 80% power. As no Minimally Clinically Important Difference (MCID) relevant to the specific context could be found for the PEI, the study is powered to find a 0.40 effect size – representative of a small to medium effect.² The expected SD for the population is 3.86¹ (taken from Howie et al. 1998) thus, the implied MCID between the groups would be a score of 1.55 scale points. Accordingly, the required sample is 100 in each arm. If we account for 20% dropout and missingness, the target recruitment is 120 in both phases 1 and 3.

6. Participant characteristics

Baseline characteristics for participants will be displayed in relation to the two groups of participants, i.e., those who are enrolled Phase 1 and those who are enrolled in Phase 3. Given the fact that patient groups are not randomly allocated hypothesis testing will be done comparing the groups at baseline for comparability.

See Tables in section 9 for details of which variables will be collected and how they will be reported.

7. Methods of analysis

Descriptive statistics:

For all outcomes, numerical variables will be summarised as either mean (SD) or median (IQR) depending on the skew of the distribution of the variable in question. Categorical variables will be described as frequencies and percentages.

Primary outcome measure:

A two-tailed independent sample t-test will be conducted to compare the mean PEI score in Phase 1 with that in Phase 3. An effect size, Cohen's Delta, and 95% confidence intervals will be reported for the mean difference between scores. A p-value will be reported with a significance level rate of < 5% leading to a rejection of the null hypothesis of no difference between the two groups.

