Model residuals will be checked for normality, if deviation is found appropriate transformations will be made to the PEI score. Exploration of patterns of missingness will be undertaken to look for potential associates with baseline. Under the assumption of Missing at Random (MAR) missing data on the primary outcome measure will be imputed via the multiple imputation by chained equation (MICE) method³. Sensitivity analysis will be conducted to assess impact of the MAR assumption. Analyses will be done with missing values both ± 1.55 scale points (the implied MCID) on the PEI – to model the potential effect of Missing Not at Random Bias (truncated between 0 – 12).

Secondary outcome measures:

Secondary outcome measures will be analysed via t-test. Effect sizes and 95% confidence intervals will be reported for all measures. P-values will be reported and a <5% rejection criterion will be utilised. No sensitivity analyses will be undertaken and no corrections for multiplicity will be made for the secondary outcomes.

Feasibility outcomes:

Only descriptive statistics for the feasibility outcomes will be reported. These will be counts and percentages with an appropriate denominator for each measure.

Technical details:

It is envisioned that R (current version 3.5.1) will be used for all analyses. The primary outcome will be analysed by the two study statisticians, unblinded. The statistical analyses and associated datasets will be kept in the appropriate section of the trial master file on the internal secure network.

8. References

1. Howie JG, Heaney DJ, Maxwell M, Walker JJ. A comparison of a patient enablement instrument (PEI) against two established satisfaction scales as an outcome measure of

primary care consultations. *Fam Pract.* 1998;15(2):165-171.

2. Cohen J. A Power Primer. *Psychol Bull.* 1992;112(1):155-159.

9. Tables/Figures

Feasibility/process outcomes

Potential participants	Phase 1 (before)	Phase 3 (after)	Total
Number of patients invited to take part			
Actual participants:			
Study consent & Completed baseline survey			
Consultation audio recording			
Clinician completed case report form in clinic			
Patient received clinic summary action plan			
Accessed goal setting module			
Patient completed 2-week FU survey			
Patient needed a reminder email for 2-week FU survey			
Patient completed 3-month FU survey			

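### Protocol 8.3 treats a confidence interval that contains a clinically meaningful difference as support for an effect, even when it also contains zero; the SAP's 5% test does not

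*Protocol*

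**What the plan says.** Protocol section 8.3 plans a formal hypothesis test for the PEI and mean differences between phases 1 and 3 with 95% confidence intervals, "with adjustment for any important differences between phase 1 and phase 3 participants, if appropriate". It then turns to a range of clinical outcomes, on which, by means of effect sizes, "the analysis will seek to identify on which outcomes the MSK-Tracker implementation has had impact". The next sentence gives the rule for reading them: "If a clinically meaningful difference on an outcome lies within the confidence interval, this will support evidence of an effect of the MSK-Tracker".

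The SAP, section 7, does not repeat that rule. For the primary outcome, "A two-tailed independent sample t-test will be conducted to compare the mean PEI score in Phase 1 with that in Phase 3", with a "significance level rate of < 5% leading to a rejection of the null hypothesis". For the secondary outcomes, also compared by t-test, "P-values will be reported and a <5% rejection criterion will be utilised", and "no corrections for multiplicity will be made for the secondary outcomes".

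Neither document adds a condition that the interval must exclude zero, and neither says which rule prevails.

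**The concern.** An interval that contains a meaningful difference and also contains zero is inconclusive: the data fit a worthwhile effect and no effect equally well. The protocol sentence counts that interval as support for the MSK-Tracker. It also rewards imprecision, because losing participants widens the interval and makes it more likely to reach the meaningful difference. The protocol itself allows for 50% dropout and missingness (section 8.1).

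What is at stake is the reporting of secondary outcomes. A report written from the protocol could list an outcome as showing an effect when the SAP's test on the same data does not reject no difference. This would happen in a non-randomised before-and-after comparison with many secondary outcomes and no multiplicity correction.

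**Working it through.** **Inputs.** From Protocol 8.1: SD 3.86, effect size 0.40, two-sided 5%, 80% power, 100 analysed per phase, 200 recruited after 50% loss. The PEI margin is also stated there: "the implied MCID between the groups would be a score of 1.55 scale points". From SAP section 5: 120 recruited per phase with 20% loss, so 120 × 0.8 = 96 analysed. From SAP section 9: 6 points on MSK-HQ as a patient-level threshold, with no SD given. Assumed here: 50 per phase (75% loss of 200), MSK-HQ SDs of 8 to 15, and meaningful differences of 0.3 to 0.6 SD.

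**The plan's own figure.** 0.40 × 3.86 = 1.544, which the plan gives as 1.55. A two-sample t-test at effect size 0.40 needs 99.08 per phase, so 100. Power at 100 is 0.804. 100 / 0.5 = 200. The sample size reproduces.

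**Formulas.** For n per phase:
- SE = 3.86 × √(2/n)
- half-width h = t(0.975, 2n − 2) × SE
- the protocol rule is met if the observed difference lies between 1.55 − h and 1.55 + h
- the interval includes zero if the absolute observed difference is below h

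**One result under both rules.** At n = 100, SE = 3.86 × √0.02 = 0.546 and h = 1.077. The protocol rule is met by any observed difference from 0.47 to 2.63, but the interval excludes zero in Phase 3's favour only above 1.08. An observed difference of 0.8 gives an interval of −0.28 to 1.88 and p of about 0.14. The protocol sentence calls that support for an effect; the SAP does not reject no difference.

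**PEI rates with no true effect.**

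| n per phase | SE | h | Rule met | Rule met and interval includes zero |
|---|---|---|---|---|
| 50 (assumed) | 0.772 | 1.532 | 49% | 47% |
| 96 | 0.557 | 1.099 | 21% | 18% |
| 100 | 0.546 | 1.077 | 19% | 17% |
| 120 | 0.498 | 0.982 | 13% | 10% |
| 200 | 0.386 | 0.759 | 2% | 0% |

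At every n, an interval excluding zero in Phase 3's favour occurs about 2.5% of the time. At n = 200, h is below 1.55 / 2 = 0.775, so at the planning SD one interval cannot hold both 0 and 1.55. Reading the rule as the upper limit reaching 1.55 gives the same null rates to three decimals. A simulation with the SD estimated (400,000 runs) gave 0.488, 0.210, 0.194 and 0.020 for the rule being met at n = 50, 96, 100 and 200.

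**PEI with a true difference of 1.55, n = 100.** The rule is met 95% of the time; the interval excludes zero 81% of the time.

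**Secondary outcomes, n = 100, no true effect (SDs and SD-unit margins assumed).** The last column is the actual conflict with the SAP.

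| Meaningful difference | Rule met | Rule met and interval includes zero |
|---|---|---|
| 0.3 SD | 44% | 42% |
| 0.4 SD | 20% | 17% |
| 0.5 SD | 6% | 3.5% |
| 0.6 SD | 1% | 0% |
| MSK-HQ 6 points, SD 8 | below 0.1% | 0% |
| MSK-HQ 6 points, SD 10 | 1% | 0% |
| MSK-HQ 6 points, SD 12 | 6% | 3.5% |
| MSK-HQ 6 points, SD 15 | 20% | 17% |

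Using 6 points as a between-group margin is an extrapolation, since the SAP uses it to classify individual patients.

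**The opposite error.** Read literally, the sentence gives no support when the interval lies wholly above the meaningful difference. With a true PEI difference of 3.10 (twice 1.55) and n = 100, that happens in about 81% of trials.

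**The case against.** The strongest reply is that the SAP already holds the right criterion. For a t-test of a mean difference, p below 5% and a 95% interval excluding zero are the same condition, so an analyst who follows the SAP would never use the protocol sentence. The wording is also soft: it speaks of supporting evidence within an exploratory aim, and the formal test is reserved for the PEI. The rule cannot be applied to most secondary outcomes, because the documents give a numeric margin only for the PEI and, at patient level, for MSK-HQ. For MSK-HQ the conflict with the SAP is nil at an assumed SD of 8 or 10. The largest rates come from the PEI, the outcome least exposed, and the 49% rests on an assumed 75% loss.

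Most of this stands as a limit on the size. It does not remove the point. The protocol states a rule for attributing an effect, the rule is wrong as written, and nothing makes the SAP prevail over it. The sentence refers to an outcome without restriction, so the PEI is not clearly exempt either.

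**Conclusion.** The concern holds and should be fixed. The protocol sentence supports a wrong inference and differs from the SAP's criterion, mainly for secondary outcomes. On the PEI planning figures with 100 per phase, about 17% of trials with no true effect would meet the protocol rule with an interval that also includes zero. That is about 87% of the null trials meeting the rule (0.169 / 0.193). The PEI rate rests on the planning SD of 3.86 and on the number analysed: the conflict disappears at 200 per phase and grows with loss. For other outcomes the size rests on assumed margins and SDs, and runs from nil to substantial. No data, sample size or primary test is affected.

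**What to change.** Replace the protocol sentence with:

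> Evidence of a difference between phases on an outcome will be judged by whether the 95% CI, from the same analysis as the reported p-value, excludes zero (two-sided 5%, as in the SAP), with its direction reported. Secondary outcomes are not corrected for multiplicity. Where a clinically meaningful difference is specified, the CI will be described in relation to it; a CI that includes both zero and that difference is inconclusive.

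The reference to the same analysis matters because the protocol allows an adjusted estimate while the SAP specifies a t-test; an interval from one and a p-value from the other could disagree. The new wording also removes the literal reading under which an interval wholly above the margin gives no support.

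The cost is one sentence in the protocol. It needs no SAP change, new margins, data or patients. Fewer outcomes will be described as showing an effect: on the PEI figures with a true difference of 1.55 and 100 per phase, 81% of intervals would qualify against 95% under the current rule, and that 81% is essentially the power the study was designed for. The 5% cut-off stays uncorrected across the secondary outcomes, as the SAP already states.
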